**B. Data Points**

Please see above for data points for REDOX analysis, DNA sequencing and disease assessment by bone marrow analysis.

**C. Study Duration**

Eligible patients will be treated with experimental drug Salsalate + standard venetoclax + decitabine (or 5-azacytidine) for 1 cycles of therapy. Responding patients will then continue on standard of care venetoclax + decitabine (or 5-azacytidine) in the observation phase of the study under supervision of their physician.

**D. Endpoints**

Primary endpoint: For testing the primary hypothesis, the toxicity of salicylate + venetoclax + decitabine during the first two cycles will be collected as primary endpoints.

Secondary endpoint: We will correspond response rates with the pattern of survival of low oxygen reactive species cells. The administration of drugs will be timed to determine if there is a measurable added effect of salicylate on the oxidative state of cells when used in combination with venetoclax + decitabine. Next generation sequencing will determine also if there is a correspondence of remission with patterns of mutation clearance and/or effects of treatment on the oxidative state of the leukemia cells.

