## 1.0 Research Design

### 1.1 Purpose/Specific Aims

To determine if the novel combination of salicylic-salicylic acid (Salsalate), venetoclax and decitabine (or alternate hypomethylating agent [HMA], 5-azacytidine] should be developed as a therapy for patients with advanced myeloid malignancies [acute myelogenous leukemia (AML); high risk myelodysplasia (MDS); or high risk chronic myeloproliferative disease] who are not candidates for standard induction chemotherapy with anthracycline + cytarabine. This is a phase 2 study to determine if the novel combination therapy is tolerated well and if biological endpoints are met. There is no control group.

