Salsalate is our choice to test in combination with a hypomethylating agent + venetoclax. Salicylates are known to inhibit oxidative phosphorylation and previous clinical trials at Rutgers-CINJ have utilized a salicylate as part of anti-leukemic therapy (1,2,6,7). Choline magnesium trisalicylate used in prior studies is no longer available commercially. In this study we will utilize salicylic acid (Salsalate) at a standard dose. The dose has been shown to result in therapeutic salicylate levels and like the choline magnesium trisalicylate is not acetylated and will not result in platelet dysfunction. This medication is often used as part of supportive care (anti-pyretic) during AML induction chemotherapy. We have shown previously that salicylate modulates the expression of many genes in the WNT and NF-kB pathways, including XIAP, an inhibitor of apoptosis (2). It has also been shown by others that salicylates have a direct mitochondrial effect that impedes oxidative phosphorylation (6,7). In this context, we will study Salsalate in combination with decitabine and

venetoclax as induction therapy for selected elderly patients with advanced myeloid malignancies such as AML, myelodysplasia (MDS) or myeloproliferative diseases with > 10% blast or blast equivalents. Patients who have received decitabine previously will be treated with 5-azacytidine as the HMA. Morphology, standard flow cytometry and next generation sequencing will be used as markers of MRD. When available, single cell DNA sequencing will be used to determine the sensitivity of individual leukemia clones to treatment. Oxidative phosphorylation status of cells will be profiled by flow cytometry to determine if response rates correspond with changes in the profile of oxidative phosphorylation and if Salsalate has independent effects on the profile.

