### 1.3 Research Design and Methods

#### A. Research Procedures

In this study we will treat patients with AML, MDS and advanced myeloproliferative disorders with decitabine, venetoclax and salsalate. 5-azacytidine may be substituted for decitabine if the patient has been previously treated with decitabine. Patients will be hospitalized for initiation of therapy (for at least 4 days). Venetoclax dose escalation in cycle 1 will follow the recommended “ramp up” to minimize the risk of tumor lysis. Salsalate will be added on day 5 of decitabine + venetoclax (or 5-azacytidine). There will be only one cycles of treatment with salsalate. The next treatment cycle will be administered under the direction of the treating physician.

Cycle 1:

- i. Venetoclax and decitabine (or 5-azacytidine) will initiate concurrently on d1; salsalate will be start on d5.
  1. Decitabine 20 mg/m^2/d IV will be administered d1-10. If 5-azacytidine is being used (if the patient has previously been exposed to decitabine) it will be administered at 75 mg/m^2/d SC or IV d1-7.
  2. Venetoclax will be dose escalated per package insert - 100 mg d1; 200 mg d2; and 400 mg d3-28.
  3. Salsalate 1500 mg PO bid will start on day 5 of decitabine (or 5-azacytidine) and be administered until and including the day of completion of the decitabine or 5-azacytidine.

Patients with WBC greater than 25,000/uL will be treated with hydroxyurea 2-3g PO bid per treating physician to obtain a WBC<15,000/uL. Once WBC is in target range the protocol treatment can be started. Hydroxyurea may be continued to sustain WBC < 15,000/uL as needed. Standard tumor lysis monitoring and prophylaxis will be used. Allopurinol (or alternate hypouricemic agent) will be started  $\geq$ 24 h prior to starting venetoclax and continued through dose escalation of venetoclax, or longer, as clinically indicated. During dose escalation of venetoclax patients will receive IV fluids, and tumor lysis laboratory studies (basic chemistry profile including calcium, phosphate, uric acid and lactate dehydrogenase) will be obtained every 8 hours.

Infectious disease prophylaxis may be used at the discretion of the patients treating physician. If anti-fungal prophylaxis is used the dose of venetoclax will be modified as outlined below. Proton pump inhibitors are mandated unless there is a contraindication. Venetoclax dosing will be adjusted if concurrent anti-infectives are CYP3A4 or Pgp inhibitors (see below).

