Pregnancy Test 	X		X
Radiographic Assessments 	X		
REDOX Blood Studies  (during first week of treatment)	X	X (pre first dose of salsalate and after 4-8 doses salsalate based on blood counts)	
BM asp and biopsy	X		X 
Blood flow cytometry/NGS (next generation sequencing) 	X	X	
Compliance Assessment			X
Survival 			

- |  |  |
|--|--|
| 
 
1. Within 1 week of enrollment.
 
2. Includes: Electrolytes, Calcium, BUN, Creatinine, Total Protein, Glucose, Albumin, Total Bilirubin, Alk. Phosphatase, SGOT/SGPT.
 
3. Includes: Total and Direct. Bilirubin, AST/ALT, Alkaline Phosphatase, Albumin, Total Protein.
 
4. Women of childbearing potential must have pregnancy test verified by BHCG within 1 week of enrollment.
 
5. Radiographic assessments will be selected by the attending physician as clinically indicated and in accordance with the criteria for tumor measurement assessments.
 
6. REDOX analysis ([name] lab) will be done on blood samples with CD34 selected blasts at baseline, after 1-5 days of treatment and following administration of of Salsalate with exact timing determined by numbers of leukemic blasts in the blood
 
7. NGS from BM will be done at baseline and after the second cycle or on any BM with leukemic cells detected as performed for clinical reasons. NGS or Single cell DNA sequencing may also be done by [name] as feasible from blood based upon disease status and resources.
 
8. Subjects will be tracked until relapse or change of therapy.
 
9. Disease status and survival status will be documented every 2 months until disease progression or start of new treatment.
 
10. End of Treatment = 45 days after the last dose of Salsalate.
 
11. Bone marrow aspirate can be performed within 14 days of anticipated next treatment cycle.
 
 |  |
|--|--|

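### The timed start of Salsalate can show a change on triple therapy, but not the added or independent effect on oxidative state that the protocol names

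*Combined protocol and SAP*

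**What the plan says.** Section 1.3 D (Endpoints) gives the aim under the secondary endpoint: "The administration of drugs will be timed to determine if there is a measurable added effect of salicylate on the oxidative state of cells". The sentence goes on to place this in combination with venetoclax and decitabine. Section 1.2 (Research Significance) says flow cytometry will be used to learn, among other things, "if Salsalate has independent effects on the profile". Section 1.1 states: "There is no control group".

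Section 1.3 A (Research Procedures) sets the drug timing:

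- Venetoclax and the HMA "will initiate concurrently on d1; salsalate will be start on d5".
- Decitabine "will be administered d1-10"; 5-azacytidine, for patients who had decitabine before, runs d1 to d7.
- Venetoclax is given as "100 mg d1; 200 mg d2; and 400 mg d3-28", with lower doses when CYP3A4 inhibitors are used.
- Salsalate, twice daily, "will start on day 5 of decitabine (or 5-azacytidine) and be administered until and including the day of completion of the" HMA.

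The REDOX blood samples in the section 1.3 A schedule are a pre-study sample and then "pre first dose of salsalate and after 4-8 doses salsalate based on blood counts". Sections 1.1 A, 1.1 B and 1.8 describe the reactive oxygen species (ROS) work as exploratory, and section 1.1 A makes it subject to feasibility.

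**The concern.** Both statements ask for an attribution: how much of the change in oxidative state is due to Salsalate over and above the backbone. The only design feature that could support this is the delayed start on d5. But the backbone does not stop or pause when Salsalate starts, and no patient passes through the same days without it.

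The protocol's own rationale makes this more than a formality. Section 1.1 B describes the low-ROS population as the main target of venetoclax, and section 1.2 links part of venetoclax's benefit to dependence on oxidative phosphorylation. The backbone is thus expected to move the quantity being measured, and nothing in the documents says its effect has levelled off by d5. If the endpoint is reported in its present words, a change caused partly or wholly by continued venetoclax and HMA could be read as a Salsalate mechanism.

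**Working it through.** The documents give no sample size, power, model or test for the REDOX data, so there is no stated figure to reproduce. The check is whether the named effect can be identified.

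**Step 1. Overlap (dosing days from section 1.3 A).**

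| HMA | HMA days | Salsalate days | Salsalate doses (twice daily) | Salsalate days that are also HMA and venetoclax days |
|---|---|---|---|---|
| Decitabine | d1–10 | d5–10 = 6 | 12 | 6 of 6 |
| 5-azacytidine | d1–7 | d5–7 = 3 | 6 | 3 of 3 |

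**Step 2. Exposure on either side of d5.** A sample taken before the first Salsalate dose follows four HMA days (d1–4) and four venetoclax days. Two of these (d3, d4) are at the full dose for patients without a CYP3A4 reduction. Four to eight Salsalate doses take 2 to 4 days. By the second sample a decitabine patient has had 2 to 4 more HMA days. A 5-azacytidine patient can have at most 3 more, and can receive only 6 Salsalate doses, so a sample after 7 or 8 doses is out of reach.

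**Step 3. Identifiability.** Let the mean ROS measure be Y0 at baseline, Y1 before Salsalate and Y2 on Salsalate. Let b1 be the backbone and time effect up to Y1, b2 the further backbone and time effect from Y1 to Y2, and s the Salsalate effect. Then

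- E(Y0) = m
- E(Y1) = m + b1
- E(Y2) = m + b1 + b2 + s

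so E(Y2 − Y1) = b2 + s. Three means carry four unknowns (m, b1, b2, s). The design matrix has rank 3, and every pair (b2, s) with the same sum fits equally well. A concurrent group on venetoclax + HMA without Salsalate, sampled at the same times, would add E(Y2) = m + b1 + b2 and bring the rank to 4 of 4.

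**Step 4. Can the earlier interval stand in for b2?** Only under an assumption such as linear drift. With Y0 at day 0, Y1 after 4 days and Y2 after 2 to 4 more, the contrast is (Y2 − Y1) − g(Y1 − Y0), with g = 2/4 = 0.5 to 4/4 = 1. With independent errors of unit variance its variance is 1 + (1 + g)² + g² = 3.5 to 6, against 2 for the plain difference. Linear drift is also hard to defend while venetoclax is being ramped up.

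**Step 5. Illustration of what drift could do.** The paired t-test and the drift sizes are assumptions, not the plan's. With s = 0, a two-sided 5% paired t-test rejects as follows (noncentral t, noncentrality = drift × √n):

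| Drift b2 (SD of paired difference) | 10 pairs | 20 pairs |
|---|---|---|
| 0 | 5% | 5% |
| 0.25 | 11% | 19% |
| 0.5 | 29% | 56% |
| 0.75 | 56% | 89% |
| 1.0 | 80% | 99% |

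More pairs make it worse, because the problem is bias and not precision.

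**Step 6. Sampling times side by side.**

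| Place | Intermediate sample | On-Salsalate sample |
|---|---|---|
| 1.3 A, schedule table | before the first Salsalate dose | after 4–8 doses |
| 1.3 A, footnote 6 | after 1–5 days of treatment | after Salsalate, timing set by blast count |
| 1.8 | after venetoclax ramp-up | after Salsalate is started |
| 1.10, footnote 6 | after venetoclax ramp-up | after 1–2 days, i.e. 2–4 doses |

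Under the 1.3 A footnote, the intermediate sample could precede full-dose venetoclax (d3) or fall on the day Salsalate starts (d5). The dose ranges in 1.3 A and 1.10 meet only at 4 doses. Each schedule lists one intermediate draw.

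**The case against.** The strongest reply is that the staggered start makes each patient their own reference, which is usual in exploratory single-arm pharmacodynamic work. The endpoint also says only that timing will help determine whether there is an effect, with the backbone named in the same sentence, and the word independent comes from the background section, not from the endpoint. All of this is fair. The pre-Salsalate sample does allow a change to be measured. It does not allow that change to be assigned to Salsalate without a no-drift or known-drift assumption, and the documents state neither.

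Three stronger readings are tempting and are not supported.

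- A reader might infer that the plan will credit the whole before/after change to Salsalate. No REDOX contrast, test or attribution rule is written down, so the rejection rates above illustrate the risk and do not describe the plan.
- A reader might infer that a false signal would drive the next trial. Section 1.5 ties the 20 patients to toxicity, and its remark about a randomised phase 2 trial does not mention ROS. The stopping rule in section 6.1 uses toxicity only.
- A reader might infer that the existing samples could isolate Salsalate by comparing ramp-up to d5 with d5 onwards. No single schedule contains both intermediate draws, which may be one draw described in two ways. The contrast would still assume equal backbone drift in both intervals.

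**Conclusion.** The concern holds in limited form. From this design, an added or independent Salsalate effect on oxidative state is not estimable. It is fully aliased with continued backbone therapy and time in every patient treated as scheduled, whichever HMA is used. This rests on the dosing days in section 1.3 A and the absence of a control group, and needs no assumption about the size of the drift.

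The consequence is an unsupported mechanistic attribution in an exploratory component. It does not touch the toxicity endpoint or the stopping rule. The exploratory label lowers the weight of the point, but does not make the effect estimable, and it sits uneasily with listing the aim under the secondary endpoint. The number of usable pairs may also fall below 20, because sampling depends on circulating blasts; patients with enough blasts left for a second sample may not be typical.

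**What to change.** 1. In section 1.3 D, restate the item as an exploratory within-patient change in ROS profile during Salsalate exposure on continuing venetoclax + HMA. Drop the added-effect wording there and the independent-effect wording in section 1.2, and state that the change will not be attributed to Salsalate alone.
2. Report the change from baseline to the pre-Salsalate sample beside the change from the pre-Salsalate to the on-Salsalate sample, descriptively only, with the number of evaluable patients for each.
3. Before that, reconcile the REDOX sampling times in the section 1.3 A table and its footnote, section 1.8 and section 1.10. Take into account that only 6 Salsalate doses are scheduled with 5-azacytidine.

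The cost is a few sentences and a weaker stated claim; no new arm or patients are needed. Adding a concurrent comparison here would not be a good trade. Splitting 20 patients 10 and 10 gives power of about 0.43 for a difference of 0.8 SD and 0.61 for 1.0 SD (two-sided 5%, normal approximation, assumed effect sizes). The later randomised trial is the natural place for that question.

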**1.4 Preliminary Data**

See above (Hypotheses, Research Question). Salicylates have been shown to modulate NF-kB gene expression (studies performed at Rutgers/CINJ) (1,2). Salicylates are known to uncouple oxidative phosphorylation (6,7). In combination these effects are hypothesized to enhance the anti-leukemic effects of combined hypomethylating agent + venetoclax therapy of AML.

### 1.5 Sample Size Justification

We propose 20 patients over the course of 3 years to assess toxicity, as outlined above. We anticipate also the use of data to support development of a larger multi-institutional randomized phase 2 trial.

### 1.6 Study Variables

#### A. Independent Variables, Interventions, or Predictor Variables

Decitabine (or 5-azacytidine, in patients previously treated with decitabine) in combination with venetoclax is a frequently used AML therapy. This study will introduce salicylic-salicylic acid (Salsalate) as the experimental agent. Standard doses of decitabine (20 mg/m^2/d IV x 10d for the first cycle and 5d for cycle 2) or 5-azacytidine (75 mg/m^2/d x 7d SC or IV for 1 cycle). Ramp up dosing of venetoclax and standard dose salsalate will be used.

#### B. Dependent Variables or Outcome Measures

Remission rate, biochemical response

### 1.7 Drugs/Devices/Biologics

*Product description: Salsalate (salicylic-salicylic acid is commercially available*

*Preparation (how the dose is to be prepared): The dose will be administered as 3 x 500 mg or 2 x 750 mg bid for a total of 3000 mg/d orally as indicated in the treatment plan.*

*Storage requirements: The tablets are stored at room temperature.*

*Route of administration: Oral tablet*

1. *Expected toxicities: Constipation, diarrhea, heartburn, tinnitus, nephrotoxicity, liver function test abnormalities, GI intolerance including abdominal pain, nausea & diarrhea, peripheral edema and somnolence.*

*Drug Interactions: no known interactions with hypomethylating agents or venetoclax; Salsalate is metabolized by conjugation to glycine and glucuronide metabolites*

#### A. Drug/Device Accountability and Storage Methods

The investigator is required to maintain adequate records of receipt, dispensing and final disposition of study drug. This responsibility has been delegated to the pharmacy. Include on receipt record (e.g. packing slip) from and to whom study drug was shipped, date, quantity, and batch or lot number. On dispensing record, note quantities and dates study drug was dispensed to and returned by each subject. Empty and partially empty containers of study drug will be disposed of in accordance with institutional policies and procedures.

### 1.8 Specimen Collection

Exploratory studies include: (i) flow cytometric characterization of malignant cells by reactive oxygen species content using labeling with CELLRox; and (ii) next generation sequencing of malignant cells. The timing of these studies will be determined by the percentage (and total number of malignant cells/uL at the following time points: (i) pretreatment; (ii) after the ramp-up of venetoclax; and (iii) after the initiation of salsalate. These studies are exploratory and logistics regarding cell number and purity are likely to determine the specific timing of studies (based on each individual patient's blood

counts). The strategy of sequential analysis of the effects of salsalate and chemotherapy on malignant cells before and during induction treatment has been successfully employed in our earlier studies. [name] [name] will supervise the analysis of cells for reactive oxygen species and [name] will supervise next generation sequencing. In selected cases with informative bulk next generation sequencing studies, single cell DNA sequencing may be performed. Specimens will be transported by one of investigators to the Biorepository. Specimens will be stored in the aforementioned labs and only accessed by lab staff or investigators. Specimens will not be banked.

### 1.9 Data Collection

Direct patient data (below) will be collected in the office or hospital by investigators.

Evaluations	Pre-Study (within 2 weeks)	Daily during treatment with decitabine or 5-azacytidine on cycle 1 (as clinically indicated cycle 2)	Prior to Cycle 2
Initial History & Physical	X		
Interim History & Physical		X	X
Toxicity Assessment		X	X

### 1.10 Timetable/Schedule of Events

Evaluations	Pre-Study (within 2 weeks)	Daily during inpatient treatment with decitabine or 5-azacytidine on cycle 1	Prior to Next Treatment
Initial History & Physical	X		
Interim History & Physical		X	X
Toxicity Assessment		X	X
ECOG Performance Status	X		X
CBC, differential, platelets	X 	X	X
Serum Chemistries 	X	X	X

Liver Enzymes 	X	X	X
EKG	X		
Pregnancy Test 	X		X
Radiographic Assessments 	X		
REDOX Blood Studies 		X (during first week of treatment)	
BM asp and biopsy	X		X
Blood flow cytometry/NGS (next generation sequencing) 	X	X	
Compliance Assessment			X
Survival 			

1. Within 1 week of enrollment.
2. Includes: Electrolytes, Calcium, BUN, Creatinine, Total Protein, Glucose, Albumin, Total Bilirubin, Alk. Phosphatase, SGOT/SGPT, Uric Acid.
3. Includes: Total and Direct. Bilirubin, AST/ALT, Alkaline Phosphatase, Albumin, Total Protein.
4. Women of childbearing potential must have pregnancy test verified by BHCG within 1 week of enrollment.
5. Radiographic assessments will be selected by the attending physician as clinically indicated and in accordance with the criteria for tumor measurement assessments.
6. REDOX analysis ([name] lab) will be done on blood samples with CD34 selected blasts at baseline, after ramp-up of venetoclax and after 1-2 days of SALSALATE as feasible based upon blood counts (leukemia cells in blood) during first cycle
7. NGS from BM will be done at baseline and after the second cycle or on any BM performed for clinical reasons. NGS or Single cell DNA sequencing may also be done by [name] as feasible from blood based upon disease status and resources.
8. Disease status and survival status will be documented every 2 months until disease progression or start of new treatment.

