Venetoclax dosing will be modified in the context of concurrent use of CYP3A4 or Pgp inhibitors. Venetoclax will be dosed at 70mg /d (if concurrent posaconazole) or 100 mg/d if there is concurrent use of other strong CYP3A4 inhibitors or 200 mg/d if use of moderate CYP3A4 inhibitors. Venetoclax will be dosed at 200 mg/d in the setting of concurrent use of moderate CYP3A4 inhibitors. Dosage should be modified and timing of dose adjusted if concurrent PgtP inhibitors are used. All concurrent meds will be reviewed and dosing schedules approved by a research pharmacist.

**TABLE 1** Commonly used CYP3A4 inhibitors

Moderate	Strong
Aprepitant	Clarithromycin
Cimetidine	Itraconazole
Cyclosporine	Ketoconazole
Erythromycin	Voriconazole
Fluconazole	Posaconazole
Verapamil	Ritonavir
Isavuconazole	Darunavir
Diltiazem	Atazanavir

If the patient has profound thrombocytopenia (< 10,000/uL at day 21 – 28 in the first cycle) a BM asp and biopsy may be performed at the discretion of the treating physician with the option to hold venetoclax. The start of the second cycle is at the discretion of the treating physician and may include modifications of decitabine/5-azacytidine or venetoclax dosing as per standard recommendations. These additional cycles (starting at cycle 2 are not considered part of this clinical trial).

Any Grade 3 or 4 non-hematologic adverse event thought to be Salsalate-related will require the dose to be held until the event recovers to Grade 2 or less. If the adverse event does not resolve within 1 week, the patient will be removed from the study. For Salsalate these events include renal insufficiency, gastritis, tinnitus, vertigo and unanticipated GI bleeding as common toxicities; the Salsalate-relatedness of other toxicities will be assessed by the research team in real time.

Patients will receive full supportive care therapies per Leukemia Tumor Study Group practices concomitantly during the study. No other chemotherapy, immunotherapy, hormonal cancer therapy, radiation therapy, surgery for cancer, or experimental medications will be permitted while the patients are participating in the treatment component of this study (first 2 cycles).

CSFs are not permitted as primary prophylactics. If, in the investigator's opinion, it is required in the presence of severe neutropenia (ANC <500/ $\mu$ l for at least 3 days or concurrent neutropenia and infection) then use of CSFs is allowed per treatment plan described above.

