All "unexpected" (defined below) and/or "serious" experimental drug related adverse events occurring during the active portion of therapy, or up to 30 days after the last dose of treatment, will be reported to the Office of Human Research Services at [contact] or [contact]. Events will be promptly reported, in writing, to the local IRB in accordance with IRB policy. If a death occurs the IRB will be notified within 24-hours of initial receipt of information. All other SAEs must be reported to the IRB within three to ten days of initial receipt of information. Written follow-up reports are required when additional information is needed to fully characterize the event. Copies of each report sent to the IRB will be kept in the study regulatory file.

In addition to reporting to the local IRB, reporting to external bodies such as industry and/or the FDA may be necessary

In the absence of treatment delays due to adverse events, treatment may continue until one of the following criteria applies:

- a) Disease progression/relapse during active treatment,
- b) Intercurrent illness that prevents further administration of treatment,
- c) Unacceptable adverse event(s).
- d) In the event of any drug-related life-threatening toxicity or laboratory abnormality the patient will be withdrawn from further treatment,
- e) Patient decides to withdraw from the study,
- f) Noncompliance with treatment plan,
- g) General or specific changes in the patient's condition render the patient unacceptable for further treatment in the judgment of the investigator, or
- h) Protocol violation - any patient found to have entered this study in violation of the protocol might be discontinued from the study at the discretion of the Principal Investigator.
- i) The desired level of compliance is  $\geq 75\%$ . Patients who cannot maintain this level of compliance may be removed from the study.

Evaluations	Pre-Study (within 2 weeks)	Daily during treatment with decitabine or 5-azacytidine	Prior to Next Treatment
Initial History & Physical	X		
Interim History & Physical		X while hospitalized	X
Toxicity Assessment		X	X
Concomitant Medications	X	X	X
ECOG Performance Status	X		X

CBC, differential, platelets	X 	X while hospitalized	X
Serum Chemistries 	X	X while hospitalized	X
Tumor lysis monitoring and treatment)		X (q8h during ramp up and qd while hospitalized)	
Liver Enzymes 	X	X while hospitalized	X
EKG	X		

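### Chemistries and liver enzymes are required on treatment only for inpatients, so a patient discharged after day 4 can have none on any Salsalate day

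*Combined protocol and SAP*

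**What the plan says.** Section 1.3 A sets the timing. On the hospital stay: "Patients will be hospitalized for initiation of therapy (for at least 4 days". On the study drug: "Salsalate will be added on day 5 of decitabine + venetoclax (or 5-azacytidine". Salsalate is given twice daily through the last day of the hypomethylating agent (HMA), which is d10 with decitabine and d7 with 5-azacytidine.

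Two tables set the laboratory schedule.

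- **1.3 evaluation table.** The on-treatment column is headed "Daily during treatment with decitabine or 5-azacytidine", but the cells for serum chemistries and for liver enzymes read "X while hospitalized". Toxicity assessment in the same column carries a plain mark with no such limit. The tumor lysis row reads "X (q8h during ramp up and qd while hospitalized".
- **1.10 schedule.** The on-treatment column is headed "Daily during inpatient treatment with decitabine or 5-azacytidine on cycle 1".

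Both tables require chemistries and liver enzymes again before the next treatment. Section 1.3 leaves the start of that cycle to the treating physician.

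Section 1.3 lists, for Salsalate, "renal insufficiency, gastritis, tinnitus, vertigo and unanticipated GI bleeding as common toxicities". Section 1.7 adds nephrotoxicity and liver test abnormalities. A Salsalate-related Grade 3 or 4 non-hematologic event requires the drug to be held, and "If the adverse event does not resolve within 1 week, the patient will be removed from the study". Section 6.1 counts a Grade 3 event toward stopping if it is at least possibly related and has not reversed within a week, subject to listed exceptions. One such event in the first 10 patients stops the trial.

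**The concern.** The laboratory requirement lapses at the earliest permitted discharge, which is the day before the experimental drug starts. A rise in creatinine or transaminases can be silent, so a daily clinical assessment need not find it. Section 4.1 C admits patients with creatinine clearance just above 30 ml/min, and section 4.7 relies on real-time toxicity monitoring and strict stopping rules to limit risk.

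Two things are at stake. The hold rule in 1.3 can act only on an event that someone has detected while Salsalate is still being given. The 6.1 count, which turns on a single event early in the trial, can include only events for which a value exists. As written, detection of renal and liver toxicity would depend on the discharge date and on what each physician chooses to order.

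**Working it through.** **Inputs.** All from 1.3 A: minimum stay d1–d4; Salsalate d5–d10 with decitabine (6 days, 6 × 2 = 12 doses) or d5–d7 with 5-azacytidine (3 days, 3 × 2 = 6 doses); venetoclax ramp-up d1–d3; venetoclax to d28.

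**1. Required panels on Salsalate days.** With a stay of L days from d1 and S Salsalate days, the number is min(S, max(0, L − 4)).

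| Stay L | Decitabine (S = 6) | 5-azacytidine (S = 3) |
|---|---|---|
| 4 | 0 | 0 |
| 5 | 1 | 1 |
| 7 | 3 | 3 |
| 10 | 6 | 3 |

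**2. Other scheduled tests.** The 8-hourly tumor lysis tests belong to ramp-up and end on d3, before Salsalate. After that they are daily only in hospital. The 1.9 table has a daily column without an inpatient limit, but its rows are history and physical and toxicity assessment, with no laboratory test.

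**3. What the next required panel catches.** Consider a Grade 3 laboratory event that starts on an outpatient Salsalate day and that nobody notices.

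- It reverses within a week: not counted under 6.1, but the hold may not have been applied.
- It lasts more than a week and clears before the next panel: it meets the 6.1 duration test but may be missed.
- It persists to the next panel: seen, although the onset date is uncertain.

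The documents give no date for that panel. As an illustration only, suppose it falls on d28, the last planned venetoclax day. Onset on d5 leaves 28 − 5 = 23 days; onset on d10 leaves 28 − 10 = 18 days. The middle group is then events lasting more than 7 days and less than 23 or 18 days. An earlier panel narrows that window and a later one widens it.

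**4. The one-week mark.** Onset on d5–d10 plus 7 gives d12–d17, which is 2 to 7 days after the last decitabine day. Onset on d5–d7 plus 7 gives d12–d14, which is 5 to 7 days after the last 5-azacytidine day. Salsalate has always ended by then, so a value at this mark can classify an event under 6.1 but cannot change Salsalate dosing.

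**5. Weight of one event in 6.1.** With a uniform prior, the posterior after k events in n patients is Beta(1 + k, 1 + n − k). At n = 10:

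- k = 0: P(rate > 7%) = 0.93^11 = 0.450, matching the printed 0.450104.
- k = 1: 0.93^11 + 11 × 0.07 × 0.93^10 = 0.4501 + 0.3727 = 0.823, matching the printed 0.82277.

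One event crosses the 80% line. This is a property of the boundary and would be true of any event; it does not measure this gap.

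**6. Toxicities exposed.** Of the Salsalate events named in 1.3, 1 of 5 is found by chemistry (renal insufficiency). Of those in 1.7, 2 of 9 are (nephrotoxicity and liver test abnormalities).

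**The case against.** The strongest reply is that the plan already follows toxicity in several ways. Toxicity assessment is daily during HMA treatment in 1.3 and 1.9 with no inpatient limit. Section 1.3 requires all adverse events up to 30 days after the last dose to be graded, with stop dates and resolution. Counted from a last Salsalate dose on d10, that runs to d40, well past d17. Recovery of a known creatinine event to Grade 2 or less cannot be shown without a repeat test. Section 6.3 has the investigator review data weekly. Both tables require a panel before the next treatment, and 6.1 counts persistent events, which are the ones that panel is most likely to show. Many patients may also stay in hospital longer than 4 days, and clinicians would probably order chemistries anyway.

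Most of this stands, and it narrows the point. Tinnitus, vertigo and other symptomatic events are covered. A laboratory event that has been recognised is followed up by implication. What remains is first detection: none of these provisions requires a blood test in an outpatient on Salsalate, and usual care is not a protocol requirement.

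A reader might infer that the missing one-week value undermines the removal rule or endangers patients. The documents do not support that, because Salsalate is finished before any such mark and known events carry their own follow-up. Nor do they support saying that renal and liver toxicity would go unseen altogether, since the later panel is required.

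**Conclusion.** The point holds for laboratory-detected toxicity in patients discharged early. Two tables agree on the inpatient limit, so it is not a slip in one heading. In the worst case the plan permits, 0 of 6 (decitabine) or 0 of 3 (5-azacytidine) Salsalate days have a required chemistry and liver panel. The consequences are possible late detection for the hold rule, and a possible undercount in 6.1 of events that last more than a week but clear before the next required panel.

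This rests on the minimum stay being used. The documents do not say how often that will happen. It is tempting to attach a change in the probability of stopping, but that would need the share of qualifying events that go undetected. The documents give no basis for such a share, and only some of the listed toxicities are exposed, so no figure is claimed. The gap should be fixed because it touches the primary objective and closing it costs little; it does not invalidate the design.

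**What to change.** In the 1.3 and 1.10 tables, require serum chemistries (including creatinine) and liver enzymes for outpatients at HMA treatment contacts during Salsalate:

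- with decitabine, at least once mid-course (about d7) and on the last HMA day (d10);
- with 5-azacytidine, on the last HMA day (d7).

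A single d7 panel is not enough with decitabine, because it would miss onset on d8–d10. Do not tie these panels to the REDOX blood draw. Its timing differs between 1.3 (first week, and after 4–8 doses) and 1.10 (after 1–2 days of Salsalate), and 1.10 makes it subject to feasibility.

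Optionally, add a footnote that any Grade 3 laboratory event still open on the last HMA day has a repeat value 7 days after onset, used only to classify the event under 6.1.

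The cost is an edit to two tables and perhaps one footnote, one or two extra tubes per outpatient, an occasional repeat draw, and a few more eCRF entries. The HMA is given IV or SC on every Salsalate day, so the main draws fall at visits that already take place. That matters in a study without financial support (4.6).
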